Primary hypotheses: Our primary measure of temporal window is delay discounting (DD). Our primary measure of alcohol consumption is self-reported drinks per day. Participants are asked to report how many standard drinks they had for the previous 24 hours on each day of the 7 day baseline and 28 day intervention period. Our secondary measure of alcohol consumption is breath alcohol samples from the remote breathalyzer. Participants will provide three breath samples daily for the 7 day baseline and 28 day intervention period. Our primary measures of demand are alpha and Q0. Alpha and Q0 are two derived outcomes from a hypothetical alcohol purchase task. Participants are asked to report the number of standard drinks they might hypothetically purchase at increasing price points. Q0 is a measure of how many drinks a participant might purchase when drinks are free (price = \$0). Alpha is a measure of the participants sensitivity to increasing prices (i.e., how quickly they decide to stop purchasing at higher prices). Our measure of craving is the Alcohol Urges Questionnaire (AUQ). Our measure of neural activity is BOLD response. We hypothesize that baseline BOLD response will be predictive of the efficacy of the intervention. We will model our primary outcome measures using a mixed-effects hierarchical model that includes day, time (pre/post intervention), and intervention group. A random effect will be included for each participant. We will include baseline BOLD response as a fixed-effect covariate in our analysis.

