Assessment sessions (sessions 2, 3, 4, 5 and 6). Participants will complete a battery of questionnaires and tasks grouped into three general categories: measures of substance use (including a urine test for drug and alcohol metabolites and a breath sample to test for recent alcohol use), clinically relevant measures including treatment acceptability, and measures of alcohol value and sensitivity. At the end of Session 6, participants will be provided alcohol treatment resources.

fMRI Scan. Investigators of the study will review safety issues related to MRI scanner with the participant and answer any questions immediately prior to entering the MRI scanner (see attached preMRI screening form). The subjects will lie still in the MRI scanner for approximately one hour. During the first several minutes acquisition of the structural scans will take place (e.g., localizer, T1-, T2-, and/or DTI-weighted), which will be followed by acquisition of the functional images. While the participant is inside the scanner, an investigator will be in constant visual observation of the participant and in between scans will use voice-communication via an intercom to assure the participant remains comfortable. The participant will also have a hand-held squeeze bulb to signal the investigators at any point in the experiment. In the event the participant wishes to be withdrawn, the investigator will take the participant out of the scanner immediately.

The fMRI session will consist of resting state scan(s).

Urine samples to assess pregnancy and recent substance use will be collected at the Addiction Recovery Research Center in restrooms designated for participant use that have built in stainless steel sample pass-throughs. Trained research personnel will provide specimen cups labeled only with study ID and will be responsible for testing the samples in a designated laboratory space using laboratory procedures to ensure validity and safety. To test the urine, specifically, we will utilize the hCG Urine Pregnancy Test Cassettes, which is a test kit for the determination of hCG (Human Chorionic

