Height: Self report height

Penn Alcohol Craving Scale: Assesses alcohol craving.

Reward Responsiveness Scale: Measures responsiveness to reward through a single component measure

Timeline FollowBack Interview (TLFB): Assesses the number of alcoholic drinks and other substances daily for the past 30 days, or since the previous assessment, whichever is fewer.

Urinalysis: Assesses substance use and/or pregnancy.

Weight: Self report weight

**8.4 What data will you collect during the study and how you will obtain them?
Please include descriptions of electronic data collection, database matching, and app-based data collection:**

All of the survey and questionnaire data will be collected using Qualtrics, online survey platforms used to develop, administer, and collect participant data in a secure password protected database. Only study personnel will have access to the survey and collected data.

The fMRI tasks will be administered using python-coded tasks, wherein the participant data will be securely collected on a password protected shared-drive hosted by FBRI.

fMRI analyses. GLM-based analysis will be performed using AFNI. We will perform slice timing correction, motion correction, and spatial smoothing (Gaussian kernel with full-width-at-half-maximum of 2.0 Å~ the voxel size). Linear regression coefficients (beta-weights) and t-statistic maps will be calculated. Since fMRI relies on neurovascular coupling, which changes due to the vasoactive properties of alcohol, nicotine, and caffeine (short term) and for vascular damage (long term for AUD individuals), we will model our data with a finite impulse response basis set rather than a “standard” HRF model.

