In the present study, we hypothesize that EFT will decrease reinforcer pathology measures in the real world over a longer time frame than has been done previously; that

is, EFT will decrease delay discounting, as well as alcohol consumption in the real world, demand, and craving compared to a control episodic thinking (CET) condition. Moreover, we hypothesize EFT will enhance activation in brain regions associated with prospection (e.g., hippocampus and amygdala) and the executive decision system (e.g., DLPFC). These analyses will help demonstrate the mechanisms by which EFT operates and contribute to the understanding of EFT as a potential therapeutic behavioral intervention.

Aims and Objectives

This SAP presents planned analysis tailored to the following three research aims:

Objective 1: We hypothesize that an intervention involving EFT will increase the temporal window, as measured through delay discounting, and decrease alcohol valuation (consumption, demand, and craving).

Objective 2: We hypothesize that an intervention involving EFT will show associated neural functional connectivity differences compared to the control condition.

Objective 3: We hypothesize that an intervention involving EFT will change the cognitive process involved in valuation and consequently the mathematical model that best describes delay discounting.

Study Design and Setting

Protocol Registration

We pre-registered this project on Clinical Trials.gov on October 14, 2019. The latest updates were made to the protocol on July 14, 2023, based on changes in recruitment criteria. The project can be located using the identifier NCT04125238.

Study design

Participants will be enrolled into the study and undergo the informed consent process (including signing of the informed consent) during Session 1. Session 2 will be baseline

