Objective 1: *We hypothesize that an intervention involving EFT will increase the temporal window and decrease alcohol valuation (consumption, demand, and craving).*

Our primary measure of alcohol use during the intervention period will be the daily self-reported number of drinks per day and the SOBERLINK breathalyzer screens. We will use generalized linear mixed models to compare the daily number of drinks between the EFT and CET groups. Mixed models is a method suited to the analysis of repeated measurement data. Here, the daily number of drinks will be modeled using a Poisson distribution. In the event the daily number of drinks exhibit over dispersion, other distributions, such as a negative binomial, will be considered. In a similar manner, dichotomous breathalyzer results data (positive or negative) throughout the 5-week field test will be analyzed as a function of intervention assignment, while accounting for time of day (morning, afternoon, evening) and repeated measures from each subject. Intrasubject correlation will be accounted for using an autoregressive correlation structure (AR(1)), since drinking days may be temporally related. In the event the AR(1) correlation structure is not representative of the data, other correlation structures will be considered. All missed assessments, although rare in our experience with similar field studies (approximately 5%), will be included as missing data. In the event of high rates of missing data, we will employ techniques consistent with the intention-to-treat paradigm, such as last observation carried forward methods or worst-case scenario (that all missing data is a positive BrAC measure).

Secondary analyses. In addition to the primary hypotheses listed above, we propose several additional analyses that will more fully characterize the behavior of our research participants and potentially lead to future research questions related to EFT in AUD. To this end, we hypothesize that EFT will result in changes (baseline versus post-intervention) in secondary outcome measures (e.g., Alcohol Withdrawal Symptoms Checklist). All these secondary hypotheses will be analyzed analogous to the primary hypothesis.

Covariate Plan:

We will test for individual differences in outcome measures for the intervention for each of these stratified variables. Therefore, we will include AUDIT score, SES, age, and gender in the analyses testing for an interaction between these variables and the intervention.

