Objective 2: *We hypothesize that an intervention involving EFT will show associated neural functional connectivity differences compared to the control condition.*

fMRI resting state analysis

Resting state seed-based analyses will be conducted with the CONN Toolbox⁴⁶. Preprocessing will include slice-timing correction, outlier detection, motion realignment, normalization to the MNI template, and spatial smoothing at 6 mm². Following this, the data will be bandpass filtered (0.008 to 0.09 Hz) and despiked. Finally, the data will be linearly detrended using CompCor with five principal components to remove white matter and cerebrospinal fluid signal. We will compute seed-based correlations to all voxels in the brain using a pre-specified set of seeds. Anatomical specification of seeds will be defined by the Harvard-Oxford atlas in the CONN toolbox. The pre-specified set will consist of nodes of the DMN (posterior cingulate cortex, medial prefrontal cortex, left angular gyrus, right angular gyrus), salience network (anterior cingulate cortex, left insula, right insula), and the left and right hippocampus. Group analyses will use a general linear model to determine connectivity differences between EFT and CET participants.

Objective 3: We hypothesize that EFT will change the cognitive process involved in valuation and consequently the mathematical model that best describes delay discounting.

The hyperbolic model, described above, is the most common cognitive model used to explain the change in discounting (D) as a function of time ($D(t)$). However, other mathematical models have been developed to explain additional neurocognitive processes in DD. We hypothesize that EFT will change either (1) the parameters in neurocognitive models fit to $D(t)$, (2) which neurocognitive model best fits $D(t)$, or (3) both which model and the value of the parameters that produce best fits to $D(t)$. We will perform hierarchical Bayesian model fits to the exponential, hyperbolic, generalize hyperbolic, quasi-hyperbolic, and double exponential models of DD. Model comparison and qualitative analysis of best fitting model parameters will be performed to evaluate the effect of EFT on neurocognitive processes underlying DD.

Software

All software, packages and their respective versions will be reported in publications.

References

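### Protocol 5.2 hypothesises that baseline BOLD modifies the effect of EFT, but neither the protocol nor the SAP writes a neural-by-group test of it

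*Protocol*

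**What the plan says.** **Protocol 5.2.** The data analysis plan names BOLD response as the measure of neural activity and states "We hypothesize that baseline BOLD response will be predictive of the efficacy of the intervention". It describes a mixed model with day, time (pre/post), intervention group and a participant random effect, then adds: "We will include baseline BOLD response as a fixed-effect covariate in our analysis". It writes no product terms of any kind.

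**SAP, Aims and Objectives.** None of the three objectives carries this hypothesis. The neural one is: "Objective 2: We hypothesize that an intervention involving EFT will show associated neural functional connectivity differences compared to the control condition". There connectivity is an outcome compared between arms.

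**SAP, Objective 1.** "We will use generalized linear mixed models to compare the daily number of drinks between the EFT and CET groups". No BOLD or connectivity term appears in this model or in the breathalyzer model.

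**SAP, Covariate Plan.** "we will include AUDIT score, SES, age, and gender in the analyses testing for an interaction between these variables and the intervention". No neural variable is listed, and the exploratory mediation list has none either.

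**What is scanned.** Protocol 8.2 describes resting-state scans only. The SAP agrees, both in its acquisition section and under Objective 2: "Resting state seed-based analyses will be conducted with the CONN Toolbox". Protocol 8.4 says otherwise: "The fMRI tasks will be administered using python-coded tasks", with a GLM using a finite impulse response basis set.

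**The concern.** A variable predicts the efficacy of an intervention if the between-arm difference changes with it. A covariate entered as a main effect shows something else: whether the variable predicts the outcome, averaged over the arms. As written, the analysis does not answer the hypothesis, and the SAP supplies no other test.

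Two things are at stake. First, if the covariate slope is read as the answer, it can mislead in either direction. Second, if an interaction is fitted later, the neural measure, the outcome and the model would all be chosen after the data are available. The measure is open because the documents reduce baseline BOLD response to no region, seed or summary, and because they disagree on whether there is a task.

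**Working it through.** Neither document gives a figure for this hypothesis, so there is none to reproduce. The check is on model terms, with an illustration of size.

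**Step 1: what each term estimates.** Let s_E and s_C be the slopes of the post value on standardised baseline BOLD in the EFT and CET arms, adjusted for the pre value. With 1:1 allocation:
- the covariate alone estimates the average, (s_E + s_C)/2;
- the group × BOLD term estimates the difference, s_E − s_C, which is the hypothesis.

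| Assumed pattern (s_E, s_C) | Average | Difference |
|---|---|---|
| Purely prognostic (0.30, 0.30) | 0.30 | 0 |
| Modifier, opposite slopes (0.25, −0.25) | 0 | 0.50 |
| Modifier, EFT arm only (0.50, 0) | 0.25 | 0.50 |

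The average therefore does not determine the difference.

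**Step 2: inputs for the illustration.** From the documents: 76 completers (Protocol 14.1) and its correlation, rounded to 0.70; 52 completers and correlation 0.5 (SAP, Sample size). Assumed: the slopes above, unit-variance Gaussian outcomes and a group effect of 0.5 SD. Each cell has at least 20,000 simulated trials.
- ANCOVA: post ~ pre + group + BOLD, then adding group × BOLD.
- Pre/post random-intercept model: covariate tested on (pre + post)/2, interaction on post − pre.

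**Step 3: share significant, 76 completers, correlation 0.70, two-sided 0.05.**

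| Truth | Covariate, ANCOVA | Covariate, pre/post | Interaction, ANCOVA | Interaction, pre/post |
|---|---|---|---|---|
| Prognostic 0.3, post value only | 93% | 28% | 5% | 5% |
| Prognostic 0.3, pre and post alike | 18% | 78% | 5% | 5% |
| Modifier 0.5, opposite slopes | 6% | 5% | 82% | 77% |
| Modifier 0.5, EFT arm only | 78% | 21% | 82% | 76% |

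Hand check of the ANCOVA interaction: residual SD = √(1 − 0.70²) = 0.714. The SE of the slope difference is about 2 × 0.714/√76 = 0.164, and 0.5/0.164 = 3.05. The normal approximation gives power Φ(3.05 − 1.96) = 86%, slightly above the simulated 82%, as expected in a small sample.

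**Step 4: ANCOVA power of the missing term for slope differences of 0.3 to 0.5.**

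| Completers, correlation | Alpha 0.05 | Alpha 0.01 |
|---|---|---|
| 76, 0.70 | 42–82% | 20–61% |
| 52, 0.5 | 21–49% | 8–25% |

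Both alphas are shown because the two sample-size sections use 0.01, while the SAP's Statistical Principles set 0.05 with multiplicity correction.

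**The case against.** **The model sentence may only list variables.** Protocol 5.2 writes no interactions, not even group × time, so a BOLD interaction may have been intended. This stands as a limit on wording: a reader might infer that the hypothesis will not be tested, but the documents support only that no test is written. It does not remove the gap. The text labels BOLD a covariate, and where the SAP wants modifiers it names four, none of them neural.

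**This is a side hypothesis.** It sits under a heading for primary hypotheses, but that paragraph also covers secondary measures. BOLD prediction is absent from the primary objective, from the hypotheses in Protocol 2.2 and from the endpoints in Protocol 4.1. The SAP already treats analyses outside its plan as secondary or exploratory. This lowers the stakes but does not define a measure or a model.

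**The covariate is not blind to every modifier.** A reader might take the 6% figure to mean that the covariate misses true modification. That holds only for exactly opposite slopes. If BOLD acts only in the EFT arm, the ANCOVA covariate is significant in about 78% of trials. The point is that a significant or null slope cannot be interpreted as evidence on modification.

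**Scan timing.** The SAP schedule table lists group assignment before the Session 3 scan, which might suggest a post-randomisation measure. The SAP's own text, Protocol 8.1 and the Protocol 11.1 table all put the scan first. The column order of one extracted table merits only a wording check.

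**Conclusion.** The point holds as a gap in specification. Protocol 5.2 states an effect-modification hypothesis, its only written use of BOLD cannot test it, and the SAP drops both the hypothesis and the covariate. The two documents therefore also disagree on whether BOLD enters the outcome models.

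That conclusion rests on the text and on the algebra of Step 1, not on the simulations. The percentages illustrate it and depend on assumed slopes, Gaussian outcomes and the documents' correlations. They do not describe the SAP's daily count model.

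A reader might infer that the main EFT–CET comparison is untouched. That cannot be said flatly, because Protocol 5.2 writes no group × time term, so even the intervention contrast is not explicit there. Nor does this point show that the main comparison is wrong. The issue should be corrected, but it is not one on which the trial's main conclusion turns.

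**What to change.** First reconcile Protocol 8.2 and the SAP (resting state) with Protocol 8.4 (tasks, finite impulse response), so that one baseline Session 3 measure can be defined. Align the SAP schedule table with its text at the same time. Then do one of the following.

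1. **Specify the test.** Name one outcome, for example delay discounting ln(k). Test group × baseline measure on the post value adjusted for its pre value, or group × time × baseline measure with all lower-order terms. Add it to the interaction list in the SAP Covariate Plan, label it exploratory, and report the estimate with its confidence interval.
2. **Delete the hypothesis** from Protocol 5.2 and decide explicitly whether BOLD stays as a covariate, so that the protocol and SAP agree.

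The cost is wording in both documents. Option 1 adds a single product term in the ANCOVA form and several in the three-way form. No new scans or visits are needed. The drawback of option 1 is the limited power shown in Step 4: a non-significant interaction would not refute the hypothesis.

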Following informed consent (Session 1), participants will complete a second session (Session 2). Sessions 1 and 2 may be on the same day. Following this session, participants will be asked to provide daily self-report assessments of previous-day drinking remotely (see below) and 3 breathalyzer samples per day for 7 days with no other study intervention taking place and their alcohol withdrawal symptoms per day. The purpose for this baseline period is to quantify baseline drinking patterns and ensure that the participant reliably responds to and conveys study information remotely. At the end of this baseline period, participants who indicated adequate patterns of drinking on at least 4 of the 7 days and successfully reported their level of drinking as requested on 5 of the 7 baseline days will be invited to continue in the study.

Following the baseline period, participants will return to the laboratory for Session 3. During Session 3, participants will complete an fMRI. Participants will be

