We will use a 3T Siemens MAGNETOM Prisma^{fit} scanner (Siemens, Erlangen, Germany) with a 20-channel head/neck coil. T1-weighted images will be acquired at $1 \times 1 \times 1 \text{ mm}^3$ resolution using 3D MPRAGE, FOV = $256 \times 256 \times 176 \text{ mm}^3$, TR/TE/TI = 1950/4.44/950 ms, FA = 12° , phase partial Fourier 7/8, slice partial Fourier 6/8, GRAPPA factor = 4 with 33 reference lines, and bandwidth = 140 Hz/pixel. Functional BOLD data will be acquired using EPI with thirty-three 4 mm interleaved slices with a 10% slice gap, TR/TE = 2000/30 ms, FA = 10° , in-plane resolution of $3.4 \times 3.4 \text{ mm}^2$, anterior-to-posterior phase encoding and a bandwidth = 2442 Hz/pixel. Participants will be instructed to keep their eyes open during the scan and direct their gaze on a white plus (+) sign centered on a black background.

Alcohol Consumption

Changes in drinks per day and the number of positive breath alcohol samples (BrAC) will be compared within subjects between pre-intervention and post-intervention. In

addition, differences in drinks per day and the number of positive BrAC samples will be compared between groups (EFT and CET). A Timeline Follow Back (TLFB⁴⁰) will be conducted during Session 2 (pre-intervention) and Session 6 (1-month follow-up) to assess the number of alcoholic drinks consumed daily for the past 30 days. During the intervention period (from Session 2 to Session 5), participants will report daily the number of alcoholic drinks consumed.

Alcohol Urges Questionnaire (AUQ)

The Alcohol Urges Questionnaire ⁴¹ will be used to assess craving for alcohol. This 8-question measure of drinking urges is scored by summing responses to a 7-point Likert scale. The dependent measure of the summed score will be compared within subjects between pre-intervention and post-intervention. In addition, differences in alcohol craving will be compared between groups (EFT and CET).

Alcohol Use Disorders Identification Test (AUDIT)

The Alcohol Use Disorders Identification Test (AUDIT⁴²) will be used to assess hazardous or harmful alcohol use. AUDIT is a 10-item screening tool that assesses alcohol consumption, drinking behaviors, and alcohol-related problems. Differences in alcohol AUDIT scores will be compared between groups (EFT and CET).

Alcohol Relative Reinforcement Schedule (ARRS)

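### The daily-drinks models leave out the 30-day drinking history taken at Session 2, giving up a modest amount of precision (no bias) on the primary consumption outcome

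*Protocol*

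**What the plan says.** **Models.** Protocol Section 5.2 says: "We will model our primary outcome measures using a mixed-effects hierarchical model that includes day, time (pre/post intervention), and intervention group". It adds a participant random effect and baseline BOLD. SAP Objective 1 says: "We will use generalized linear mixed models to compare the daily number of drinks between the EFT and CET groups". It specifies Poisson (negative binomial if overdispersed) and AR(1). The SAP Covariate Plan adds: "we will include AUDIT score, SES, age, and gender in the analyses testing for an interaction between these variables and the intervention". TLFB appears in none of these, and the SAP names no prior-drinking covariate.

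**Drinking history.** The SAP (Data Measures, Alcohol Consumption) has the TLFB "conducted during Session 2 (pre-intervention) and Session 6 (1-month follow-up) to assess the number of alcoholic drinks consumed daily for the past 30 days". Protocol Section 8.3 lists the instrument as: "Assesses the number of alcoholic drinks and other substances daily for the past 30 days, or since the previous assessment, whichever is fewer". It names no session.

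**Baseline week.** Drinks are self-reported on "each day of the 7 day baseline and 28 day intervention period" (Protocol Section 5.2). Protocol Section 8.2 says: "The purpose for this baseline period is to quantify baseline drinking patterns". The same section lets a participant continue with 5 of 7 reports, provided drinking was adequate on at least 4 of the 7 days. The SAP (Participant Retention) adds a quantity rule and expects 75% to pass.

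**Balancing.** The SAP balances randomisation on square-root drinks per day and baseline discounting rate. Neither document says whether drinks per day comes from the TLFB or from the baseline week.

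**The concern.** In a small trial, a good pre-randomisation measure of the outcome is the cheapest source of precision. Here the baseline week is short, may be incomplete, and is truncated by the continuation rule. All three weaken it as a predictor of later drinking. A month of daily drinking history, collected before that week and outside the rule, is left unused.

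What is at stake is the standard error of the EFT-CET difference in self-reported drinks. The SAP sizes the trial at 52 completers and expects 54; the Protocol says 76. Timing also matters: the SAP (Statistical Principles) treats analyses added after data collection as secondary or exploratory, so a covariate chosen then could not support the primary result.

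**Working it through.** **1. Timing.** Session 2 precedes the baseline week, and group assignment follows that week in both documents. A TLFB taken at Session 2 is therefore a legitimate baseline covariate.

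**2. The plan's own figures.** Neither document gives a day-to-day or between-person variance for drinks, so there is no planned figure to reproduce on this point. The nearest is Protocol Section 14.1, an ANCOVA with a pre-post correlation of about 0.70. With d = 0.5 (f = 0.25), two-sided alpha 0.01 and 95% power, n per arm = 2 × ((2.576 + 1.645)/0.5)² × (1 − 0.70²) = 142.5 × 0.51, or 73 per arm, not the stated 38. That mismatch is a separate matter. It is relevant here only because it shows that the sizing leans on a strong baseline covariate.

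**3. Formula.** Let B be the baseline-week mean, T the TLFB mean and P the 28-day mean. The variance of the adjusted group effect is proportional to 1 − R², so the effect of adding T is

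ratio = (1 − R²(B,T)) / (1 − R²(B)), where R²(B,T) = (r_BP² + r_TP² − 2·r_BP·r_TP·r_BT) / (1 − r_BT²).

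**4. Worked case (assumed inputs).** Daily intraclass correlation 0.3, no autocorrelation, 7 reports, and true-mean correlations of 0.8 both pre versus post and TLFB versus daily report.

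- Variances: B = 0.3 + 0.7/7 = 0.4000; P = 0.3 + 0.7/28 = 0.3250; T = 0.3 + 0.7/30 = 0.3233.
- r_BP = 0.24/√(0.4000 × 0.3250) = 0.6656.
- r_BT = 0.24/√(0.4000 × 0.3233) = 0.6674.
- r_TP = 0.3 × 0.8 × 0.8/√(0.3233 × 0.3250) = 0.5923.
- R²(B) = 0.4431; R²(B,T) = 0.4826.
- Ratio = 0.5174/0.5569 = 0.929, a 7% reduction.

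Over intraclass correlation 0.3-0.5, autocorrelation 0 or 0.3, and both true-mean correlations 0.8-0.9, the ratio runs from roughly 0.8 to 0.97 with 7 reports, and down to about three-quarters with 5.

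**5. Simulation with the continuation rule.** Assumptions: mean about 5 drinks/day; between-person log-SD 0.4-0.6; negative-binomial size 1.5-4; person-level change into the intervention period log-SD 0.3-0.5; TLFB recall error log-SD 0.15-0.3. From the SAP: its drinking-day and quantity rule, and about 5% missing reports. There were 16 settings, on the square-root scale, with one degree of freedom charged at 52 completers. Reductions are relative to adjustment for the baseline week alone.

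| Assumed person-level shift between TLFB and baseline week | Variance reduction | Median |
|---|---|---|
| None | 2-26% | 9% |
| log-SD 0.3 | 0.5-14% | 5% |
| log-SD 0.4 | about 0-11% | 3% |

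Poor recall (log-SD 0.4) with no shift gives about 0-11%. With a shift of 0.3 and AUDIT already in the model (assumed correlation 0.4), the median is 4%. The rule passes 57-68% of simulated people, against the SAP's expected 75%, so these inputs truncate the week somewhat harder than the sponsor expects.

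**6. Power.** For a contrast with 80% power, new power = Φ((z + 0.8416)/√ratio − z). At two-sided 0.05 (z = 1.960), ratios 0.95 and 0.90 give 82% and 84%. At 0.01 (z = 2.576) they give 82% and 85%. In completers, 54 × (1/0.95 − 1) = 2.8 and 54 × (1/0.90 − 1) = 6.0, so the gain is worth about 3 to 6 extra people.

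**The case against.** **It is an optional refinement.** A plan need not use every correlated baseline variable, and omitting this one biases nothing. That stands. A reader might infer that selecting people on the baseline week distorts the EFT-CET comparison. The documents do not support that: the rule acts before randomisation and equally on both arms. It does cause regression to the mean in the within-arm pre/post comparison (simulated mean drinks fell 6-14% with no intervention effect), but that is a different comparison.

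**The gain is measured against an analysis nobody planned.** The reductions are relative to a model already adjusted for baseline-week drinks, which neither document specifies for daily drinks. This also stands, and it makes the remedy more than a one-term edit.

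**The gain could be small.** Participants want to quit or cut down, and daily monitoring starts after the TLFB, so drinking may shift between the two. AUDIT, already among the SAP covariates, carries some of the same information. A reader might take the upper end of the range (26%, or 80% power rising to about 90%) as the expected benefit. That requires stable drinking and good recall, which the documents do not establish. Likewise, 5 reports is the minimum for continuing; the SAP expects only about 5% of assessments to be missed.

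**Balancing may already use TLFB.** One might assume that the balancing variable is baseline-week drinks, but the source is unstated. If it is TLFB, some of the gain may be captured in the design, although an analysis that ignores the balancing variable would not show it in the standard error.

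**Conclusion.** The point holds as a missed efficiency gain, not as an error that threatens validity. Adding the TLFB mean to baseline-week adjustment would reduce the variance of the EFT-CET effect on daily drinks by roughly 0-26%, typically about 5-10%, taking 80% power to about 82-84%. The direction is dependable, since nearly every setting tried showed some gain. The size rests on assumed variance components, recall error and stability of drinking, and cannot be derived from the documents. The Session 2 timing rests on the SAP alone. No gain has been quantified for the breath-alcohol model, so none is claimed.

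**What to change.** In SAP Objective 1, before the data are analysed:

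- Estimate EFT versus CET on the 28 intervention days, with two pre-specified fixed covariates: the baseline-week mean drinks per day and the Session 2 TLFB mean drinks per day, both on the square-root or log scale.
- State in the Randomization section which source supplies the drinks-per-day figure used for balancing.
- Name Session 2 for the TLFB in the Protocol's measures list, so that the two documents agree.
- Using the TLFB covariate in the breath-alcohol model is optional.

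Cost: no new data and one degree of freedom for TLFB. Moving to a 28-day analysis with baseline adjustment is a larger edit, because it replaces the Protocol's pre/post formulation for daily drinks; Protocol Section 5.2 should be brought into line.
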